#### **Specific Aims:**

This UW-CTRI study is designed to assess whether completely electronic, EHR-based, closed-loop referrals for tobacco cessation (eReferral) from primary care clinics to a state telephone tobacco quitline can increase the number/percentage of adult tobacco users receiving evidence-based tobacco dependence treatment when compared to paper-based, manual fax referrals.

2/28/2017 Amendment: The specific aim of this extension of the protocol is to evaluate the extent to which electronic, closed-loop eReferral to SmokefreeTXT in up to 3 primary care clinics engages patients who smoke in the program, retains these individuals in the 6-week duration of the program, and helps them to quit smoking as assessed via self-report at the end of the 6-week program.

**Primary Aim 1:** To evaluate the rates of referral of tobacco users visiting primary care clinics to the WTQL, comparing those who were referred via an EHR-based electronic referral system vs. those referred via a manual paper fax referral system. Analyses will address the change in referrals from pre- to post-intervention and the trajectory of referral post-intervention per clinic.

**Primary Aim 2:** To evaluate the rates of quality referrals of tobacco users visiting primary care clinics to the WTQL, comparing those who were referred via an EHR-based electronic referral system vs. those referred via a manual paper fax referral system (quality referrals are defined as ones that result in individuals who enroll in and receive WTQL counseling and/or medication treatment services). Analyses will address the change in referrals from pre- to post-intervention per clinic.

2/28/2017 Amendment: The primary aim of the SmokefreeTXT eReferral project is to examine uptake (initial enrollment), retention (continuing engagement through the end of the 6-week program), and effectiveness (in terms of abstinence 6-weeks after the target stop-smoking date) of eReferral to SmokefreeTXT among primary care patients referred by clinic staff during clinic visits.

**Secondary Aim 1:** To examine variation in referral rates across clinics to test the hypothesis that the eReferral system will result in greater consistency in referral in addition to higher rates of referral. Nonquantitative methods will be used to understand the sources of variation.

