The analysis of the primary outcome is designed to show differences in the rate at which patients are referred to the Wisconsin Tobacco Quitline by the 12 control (F2Q) versus the 12 experimental (EHR referral) clinics during the post-intervention period. We will use a mixed effects logistic regression model via Generalized Estimating Equations (via SAS PROC GENMOD; for a population based model) with coding for the baseline and post-intervention phases, and with coding for each post-intervention monthly time point with the models centered at the 6-month post-intervention mark. Based on data from the healthcare systems, we anticipate that on average, each clinic will see about 120 smokers/month, and based upon the urn randomization procedure we expect similar smoker flow rates across the two experimental conditions. The binary dependent variable will be measured at the smoker level, i.e., whether or not a smoker seen at a clinic is referred to the quitline, and aggregated to the clinic level to constitute clinic referral rate. Thus, while clinic is the unit of analysis, our sample is the smoker, each one being one Level 1 unit. Experimental condition will be coded with a single dummy variable. The baseline WTQL referral rate data for each clinic will serve as a covariate (only one covariate will be used to preserve degrees of freedom). We will specify a logit link function and assume a first-order autoregressive structure (to address dependence across measurement occasions). We will test the main effects of experimental conditions. Further, we have an a priori plan to test for post-intervention change over time within each experimental condition and will test for interaction between experimental condition and measurement occasion. Similar analyses will be used for the quality referral outcome.

In a subsequent model we will analyze cessation rates of tobacco patients identified as smokers during a clinic visit. Abstinence will be measured at the smoker level and aggregated to the clinic level by the WTQL to determine a clinic quit rate. We anticipate that there will be no overlap in rates of abstainers/clinic (abstainers from a clinic/smokers presenting to clinics within the relevant time period) for the two experimental conditions, permitting use of a non-parametric analysis of outcome (e.g., Mann-Whitney U).

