2/28/2017 Amendment. Given that the objective of the SmokefreeTXT eReferral pilot study is to assess the feasibility, uptake, retention, and quit rates of this program, there are no specific quantitative hypotheses to test or comparisons to be conducted. Instead, analyses will be descriptive and will focus on uptake, retention, and quit rates by clinic. We will also assess staff knowledge of smoking cessation treatments and SmokefreeTXT-specific knowledge, practices, and attitudes prior to and after six months of SmokefreeTXT eReferral, with the expectation that knowledge, positive attitudes, and treatment practices among clinic personnel will improve from pre- to post-launch. In addition, we will document implementation challenges and solutions to inform future evaluation or dissemination efforts.

**Power Analyses for Intervention Phase:** Power was calculated for a two-group cluster-randomized design with clinic as the unit of randomization (n=6 clinics per group for each health system) with a conservative estimate of approximately 90 smokers seen in each clinic per month. The dependent variable for the power analysis is the proportion of smokers referred/month. We based our estimates of

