the mean number of monthly referrals in each group on pilot data from an eReferral demonstration project (Adsit et al., 2014) which found a rate of 14% for an eReferral system versus 0.3% for a paper fax referral system^4. To achieve a more conservative power analysis, we calculated power to detect a smaller difference between the groups. More specifically, we estimated power to detect a group difference on proportion referred per month with values of 2% for the Fax to Quit group versus 7% for the eReferral group. As shown in Table 3, the groups are not expected to differ at baseline (mean of 1% referrals per month for each group). As such, the power analysis was based on a test of the difference between groups for the post-intervention proportion of referrals per month (2 vs 7%). The following power analysis therefore should be conservative since it does not take advantage of baseline referral rate to index change and its projected effect size is considerably less than might be expected based on prior research. For purposes of power analysis, we assumed that the standard deviation for the mean proportion of referrals per month will be 2.5%; we also set alpha at .05 for a two-tailed test. The power analysis was computed via an online program, GLIMMMPSE, that permits power estimation for cluster-randomized designs. Results of the power analysis showed that there is >90% power to detect a mean difference of 1 versus 7% of smokers referred per month. The demonstration of this effect within two health systems will allow even greater confidence in these primary outcomes.

**Table 3. Predicted Mean Rates of Quitline Contacts/Clinic/Month as Proportions of Smokers Seen, Two Arms Across Baseline and Intervention Phases**

Intervention Arm	Baseline	Intervention
Fax Referral (Fax to Quit)	1%	2%
EHR-based Referral (eReferral)	1%	7%

2/28/2017 Amendment. Formal power analyses were not conducted for the pilot test of the feasibility of eReferral to SmokefreeTXT that will be conducted in 1-3 clinics.

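### The a priori tests of post-intervention change over months are under-specified: the wording allows month indicators or a numeric term, and no variance estimator, test or small-sample reference is named for 12 clinics per arm

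*Combined protocol and SAP*

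**What the plan says.** Primary Aim 1 (Specific Aims) covers the pre-to-post change in referral and also "the trajectory of referral post-intervention per clinic". The part of the protocol on dependent variables adds that the public-health case rests partly on referral that lasts.

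The section Hypotheses & Analytic Plan for Intervention Phase compares the "12 control (F2Q) versus the 12 experimental (EHR referral) clinics" with a logistic GEE in PROC GENMOD, an AR(1) structure and one covariate (the clinic's baseline referral rate). Time enters through "coding for each post-intervention monthly time point with the models centered at the 6-month post-intervention mark". As an a priori step the authors will "test for post-intervention change over time within each experimental condition and will test for interaction between experimental condition and measurement occasion".

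The section does not say whether month is categorical or numeric, how many degrees of freedom the time tests have, whether the variance is robust or model-based, whether tests are Wald or score, or whether a small-sample correction applies. The power section covers only the between-arm difference in referral.

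Follow-up length is also unsettled. Section I of the Methods has referrals monitored for 6 months after the initial training. The same section, Table 1 and the Implementation Phase paragraph give a 12-month implementation phase.

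**The concern.** The time sentence can be read in two ways. Separate coding of each month, and an interaction with measurement occasion, suggest month indicators. Centring at month 6 suggests numeric time. The within-condition test then has 1, 5 (6 months) or 11 (12 months) df, on 12 clinics. The interaction has the same df on 24 clinics.

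A robust covariance matrix built from 12 clinics supports few contrasts. With 5 or 11 of them, a Wald test referred to chi-square rejects far too often, and a score test with empirical variance rejects far too seldom. With the choice left open, a finding of waning referral, or of different trajectories in the two arms, could depend on an option picked after the data are seen.

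**Working it through.** **Inputs from the documents.** 12 clinics per arm ("n=6 clinics per group for each health system", two systems); "we also set alpha at .05 for a two-tailed test"; "values of 2% for the Fax to Quit group versus 7% for the eReferral group"; "standard deviation for the mean proportion of referrals per month will be 2.5" percent; 90 smokers per clinic-month (power section) or 120 (analysis section); 6 or 12 post-intervention months.

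**The plan's own figure.** For 2% versus 7%, SE = 2.5 × √(2/12) = 1.02 points, and 5/1.02 = 4.90. Power is Φ(4.90 − 1.96) = 99.8% (normal) or 99.7% (noncentral t, 22 df). The stated power above 90% holds for the 24-clinic comparison. It says nothing about the time tests.

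**Robust Wald test, closed form.** Take a model with a separate rate for each arm and month, equal clinic sizes, approximate normality and no true trend. With q contrasts the uncorrected robust Wald statistic W is a scaled F:

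- within arm: W = [12q/(12 − q)] × F(q, 12 − q)
- interaction: W = [24q/(23 − q)] × F(q, 23 − q)

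True size is the chance that W exceeds the 5% chi-square point c.

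| Month coding | c | Within arm | Interaction |
|---|---|---|---|
| Indicators, 6 months (q = 5) | 11.07 | P(F(5,7) > 1.29) = 36.5% | P(F(5,18) > 1.66) = 19.5% |
| Indicators, 12 months (q = 11) | 19.68 | P(F(11,1) > 0.149) = 97.5% | P(F(11,12) > 0.894) = 57.0% |
| One numeric term (q = 1) | 3.84 | P(F(1,11) > 3.52) = 8.7% | P(F(1,22) > 3.52) = 7.4% |

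For example, 1.29 = 7 × 11.07/60 and 1.66 = 18 × 11.07/120.

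**Robust score test.** The statistic is about W/(1 + W/K), so it cannot exceed K, the number of clinics used: 12 within arm, 24 for the interaction.

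- Within arm, 6 months: rejection needs W > 11.07/(1 − 11.07/12) ≈ 143, so size is P(F(5,7) > 16.7) = 0.09%.
- Within arm, 12 months: the ceiling of 12 is below 19.68, so rejection is impossible.
- Interaction: size 3.5% (6 months) and 0.5% (12 months). The ceiling of 24 is above both critical values.
- One numeric term: 4.4% within arm, 5.3% for the interaction.

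**Simulation under flat trajectories.** AR(1) logistic GEE with the baseline covariate, 600 trials in each of 8 settings (6 or 12 months; 90 or 120 smokers per month; with or without extra monthly noise). Assumptions not in the documents: fax-arm clinic SD 1.25%, baseline SD 0.6%, extra monthly logit noise SD 0 or 0.4.

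| Test | Within arm | Interaction |
|---|---|---|
| Indicators, robust Wald, 6 months | 37–48% | 25–29% |
| Indicators, robust Wald, 12 months | 97–99.5% | 74–78% |
| Numeric, robust Wald, uncorrected | 7.7–12.8% | 7.2–9.3% |

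Over both kinds of test, model-based AR(1) variance with indicators gave 0.8–11.7%, and the numeric term with a t reference and small-sample correction gave 3.7–7.7%. With 600 trials the Monte Carlo standard error near 5% is √(0.05 × 0.95/600) = 0.9 points.

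**Simulated power.** 90 smokers per month, 400 trials per setting, with eReferral referral declining from 10% to 5%:

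- Numeric term, t reference: within arm 99.5% (6 months) and 100% (12 months); interaction 65% and 86%.
- Indicators, robust score, 6 months: 5.8% within arm and 9.8% for the interaction (28% and 50% for a steeper decline, 12% to 3%).
- Indicators, robust score, 12 months: no rejections in either decline.

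**The case against.** A reader might infer that the plan commits to multi-df robust tests that reject falsely in 20–98% of trials or cannot reject at all, so that the trajectory part of Primary Aim 1 cannot be judged. The documents do not support that, for four reasons.

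- **Coding.** Centring has its natural meaning for numeric time. Trajectory and change over time fit a slope at least as well as an omnibus test. A section that allows one covariate in order to save degrees of freedom sits badly with 11 month indicators and 11 interactions.
- **Variance and test.** The section names neither a robust variance nor a Wald test, and model-based tests stayed within 0.8–11.7% even with indicators.
- **Follow-up.** The 11-df figures need 12 monitored months, where one statement gives 6.
- **Inability to reject.** Of the four indicator score tests, only the 12-month within-arm test is strictly barred from rejecting.

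All four stand, and they limit the large figures to one reading of the plan. They do not make the numeric reading safe as written: an uncorrected robust Wald test is oversized on 12 clinics per arm even at 1 df.

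A further objection is that a linear term is only one choice. Curvature is plausible after a launch training and a one-month refresher. That is fair, and it is the real cost of the change.

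**Conclusion.** The concern holds as a specification gap in the a priori time tests of a primary aim. Under month indicators with an uncorrected robust Wald test, size is 36.5% or 97.5% within arm and 19.5% or 57.0% for the interaction (6 or 12 months). Under indicators with a robust score test, the within-arm test has about 0.1% size at 6 months and cannot reject at 12. Under a numeric month term the trajectory can be judged, with size 8.7% and 7.4% if the robust Wald test is left uncorrected (simulated up to 12.8%) and near 5% with a t reference.

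The closed forms assume equal clinic sizes and approximate normality. The simulations rest on the variance assumptions listed above. The between-arm main effect is a single-df test, so the multi-df problem does not reach it. The gap should be closed before analysis; it does not threaten the main comparison.

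**What to change.** In Hypotheses & Analytic Plan for Intervention Phase, state that:

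- the formal trajectory tests use one numeric month term on the logit scale, centred as planned;
- change within each condition is a 1-df slope with a t reference on 11 df;
- the condition-by-time interaction is a 1-df slope difference with a t reference on 22 df;
- both use a robust variance with a named small-sample correction;
- month-specific rates are plotted by condition as description.

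Reconcile the 6-month monitoring statement in section I of the Methods with the 12-month phase there, in Table 1 and in the Implementation Phase paragraph, so that the months entering the model are fixed.

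The cost is a sentence or two and no new data. The downside is that a curved trajectory would be shown but not formally tested.

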**Secondary Aim 2:** To evaluate smoking abstinence rates of tobacco users who were referred to and accepted services from the WTQL, comparing those who were referred via an EHR-based referral system vs. those referred via a manual paper fax referral system. Analyses will address 7-day point prevalence smoking outcomes at 4-months after participant registration with the WTQL and will reflect per clinic rates.

**Secondary Aim 3:** To assess clinician and staff satisfaction with the eReferral and paper F2Q systems.

2/28/2017 Amendment: A secondary aim of the SmokefreeTXT eReferral project is to gather information about the process of implementing eReferral to SmokefreeTXT in primary care clinics, particularly regarding clinic staff implementation of and satisfaction with the SmokefreeTXT eReferral system.

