For both the F2Q and eReferral systems, data acquisition to establish WTQL referral rates will be derived from monthly reports to UW-CTRI from the WTQL. Referral rates are based on a denominator reflecting the number of adult tobacco users seen in the study clinics per month during the study time periods; this will be obtained for both referral systems by querying an existing EHR field for all clinic EHR systems that reflect response to an existing vital signs question regarding tobacco use. Such data will be available for both the baseline and post-intervention periods. Thus, the method and presumably the reliability of the data acquisition process will be equivalent across the two study arms.

In order to obtain data for the secondary analysis of smoking abstinence among referred participants, the study will use standard WTQL follow-up evaluation procedures. The standard procedure of the WTQL is to obtain consent to conduct follow up as part of each registration process. The tobacco quitline routinely conducts follow up evaluations of quitline users for QI and self-evaluation purposes four months post registration. Per the study team's request, aggregate follow-up data of four-month 7-day point-prevalence self-reported smoking status, quitting intentions, and other tobacco and tobacco cessation medication use on up to fifty patients completing the follow-up per clinic will be provided to study staff. Cessation rates will be projected separately by the number of tobacco patients visiting each clinic, those referred for quitline services, and those who enroll in WTQL following referral for both the paper faxed-based and EHR-based referral systems. Only patients who register for and agree to be followed up by the quitline will be contacted by the quitline for follow up.

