2/28/2017 Amendment. As in the existing protocol, aggregated EHR data will be gathered to determine the number of patients seen per clinic per month in the study, including the number of tobacco using patients seen, and this will be used as the denominator in calculations of the rate of eReferral to SmokefreeTXT. In contrast to the existing protocol evaluating eReferral to the Quitline, there will be no comparison condition in this pilot study. Analyses will focus on the rate of uptake (eReferrals), drop out during the 6-8 week program, and smoking status at six-weeks post-quit. Assessment of smoking status six weeks post-quit is standard practice in the SmokefreeTXT program, along with assessment of smoking status, reset quit dates, craving, mood, and slips throughout the program. As such, there are not additional assessments proposed for the research study; all are standard parts of the SmokefreeTXT program. Data shared for eReferral evaluation purposes will be deidentified and/or aggregated.

**Hypotheses & Analytic Plan for Intervention Phase:** Specific quantitative hypotheses to be tested are-

- The fax referral training and the EHR-based referral training and intervention will both increase tobacco user quitline referrals and contacts, and quality referrals and contacts, during the post-intervention period relative to the baseline period. This pattern will be seen when examining monthly and aggregate /clinic data.
- The EHR-based referral intervention will be more effective than the fax referral intervention in increasing tobacco user quitline referrals and contacts, and quality referrals and contacts, in the post-intervention period relative to the baseline period. This superiority will be seen in /clinic data. Thus, while both interventions will increase contacts relative to baseline, the EHR-based referral will be especially effective in this regard.

Note that this second hypothesis implies the presence of an interaction between intervention condition and the two experimental periods (baseline and post-intervention).

- The EHR-based referral intervention process will increase smoking cessation outcomes more than does the fax referral mechanisms during the post-intervention phase. This will be seen when examining quit rate/clinic data.

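### The only cessation test counts quits seen among quitline registrants over all smokers seen, so a difference does not by itself show added cessation, and its denominator is not that of Secondary Aim 2

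*Combined protocol and SAP*

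**What the plan says.** Secondary Aim 2 (Specific Aims) is "To evaluate smoking abstinence rates of tobacco users who were referred to and accepted services from the WTQL", compared between referral systems. It adds: "Analyses will address 7-day point prevalence smoking outcomes at 4-months after participant registration with the WTQL and will reflect per clinic rates".

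The section on dependent variables for the intervention phase says how abstinence is obtained: "Only patients who register for and agree to be followed up by the quitline will be contacted by the quitline for follow up". Data come back "on up to fifty patients completing the follow-up per clinic will be provided to study staff". The same section says: "Cessation rates will be projected separately by the number of tobacco patients visiting each clinic, those referred for quitline services, and those who enroll". That gives three denominators (smokers seen, referred, enrolled), with no test attached to any of them.

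The third hypothesis in the analytic plan is causal: "The EHR-based referral intervention process will increase smoking cessation outcomes more than does the fax referral mechanisms during the post-intervention phase". It is to be judged on clinic quit rates.

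The analytic plan then describes one cessation analysis. The quitline aggregates abstinence to clinic level, and the rate is abstainers over all smokers presenting: "We anticipate that there will be no overlap in rates of abstainers/clinic (abstainers from a clinic/smokers presenting to clinics within the relevant time period". The expected separation is given as the reason for a non-parametric test, with Mann-Whitney U as an example.

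**The concern.** The numerator can contain only smokers who registered and were followed. The denominator contains everyone who smokes and was seen. A smoker who quits without registering counts as not abstinent. The share of smokers whose quitting can be seen at all is therefore set by referral and enrolment, which the intervention is designed to increase.

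A higher rate under eReferral then mixes two things: quits that happened because more people received the service, and quits that would have happened anyway but are now recorded. The planned comparison cannot separate them, yet a significant result would be read as support for the third hypothesis.

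The tested rate also has a different denominator from Secondary Aim 2, which is limited to people who accepted services. The enrolled rate that matches the aim is listed but has no test.

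**Working it through.** **The plan's own figure.** No power or expected quit rate is stated for cessation. The stated power (above 90%) is for referral. With 12 clinics per arm, 2% vs 7% and SD 2.5 points, z = 5 / (2.5 × √(2/12)) − 1.96 = 2.94, or 99.8% power. The statement holds as a lower bound, but says nothing about quitting.

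**Inputs from the protocol.**
- Referral: "values of 2% for the Fax to Quit group versus 7% for the eReferral group" (Power Analyses).
- Enrolment after fax referral: 41% (The Paper Fax-to-Quit Tobacco Quitline Referral System). No eReferral figure is given.
- Smokers per clinic per month: 90 (Power Analyses) or 120 (analytic plan).
- Months: 6 of referral monitoring, or a 12-month implementation phase (both in Methods for Evaluating the eReferral Mechanism). I ran 90 × 6 = 540 and 120 × 12 = 1,440 smokers per clinic.

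**Assumptions.** Quit probabilities, eReferral enrolment, the fraction followed, the ICC, and the use of 2.5 points as the between-clinic SD of referral.

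**Step 1: share of smokers whose quit can be seen.** Fax: 0.02 × 0.41 = 0.82%. eReferral: 0.07 × 0.41 = 2.87%. Ratio 3.5 at any common quit probability. If eReferral enrolment is 30%, 0.07 × 0.30 / 0.0082 = 2.6; if 20%, 1.7.

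**Step 2: observed against added quitting.** Let q1 be the extra enrollees' quit probability with the quitline and q0 without it. The extra enrollees are 2.87% − 0.82% = 2.05% of smokers seen. Observed difference = 2.05% × q1; added quitting = 2.05% × (q1 − q0). With q1 = 30%, the observed difference is 0.62 points. Of this, 0.62, 0.41 or 0 points is added if q0 is 0, 10% or 30%. The documents give neither value.

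**Step 3: rejection rates.** Simulation with 12 vs 12 clinics, beta-distributed clinic referral rates, binomial registrants and abstainers, the fifty-completer cap, and a two-sided Mann-Whitney test at 0.05. With q1 = 30%:

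| | q0 = 0 | q0 = 10% | q0 = 30% |
|---|---|---|---|
| Planned rate, 90 × 6 | 94% | 94% | 94% |
| Planned rate, 120 × 12 | 98% | 98% | 98% |
| Every smoker's status known, 90 × 6 | 94% | 10% | 5% |
| Every smoker's status known, 120 × 12 | 98% | 20% | 5% |

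The planned rows are constant because q0 never enters the observed data. With equal referral (4.5% in both arms) rejection is 4% to 5%, so the test's size is sound.

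**Step 4: sensitivity at 90 × 6, q1 = 30%.** Rejection is about 76% if eReferral enrolment is 30%, and about 41% if 20%. If half of registrants are followed, it is 84% when completers are scaled to all registrants and 83% when they are not.

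**Step 5: the registrant comparison.** Expected registrants at 90 × 6: 540 × 12 × 0.0082 = 53 and 540 × 12 × 0.0287 = 186. The 95% half-width at 30% quitting is 1.96 × √(0.21 × (1/53 + 1/186)) = 14 points before clustering, and 15 to 18 points at an ICC of 0.01 to 0.05. At 120 × 12, about 135 and 457 remain usable after the cap: ±9 points before clustering. Fax clinics with no registrant: 27% (90 × 6) and 16% (120 × 12) at SD 2.5; 5% and 0.4% at SD 1.0.

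**Step 6: chance of no overlap at 20% to 30% quitting.** About 1% (at most 2%) at 90 × 6. At 120 × 12 it is about 2% to 4% with SD 2.5 and about 8% to 20% with SD 1.0.

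**The case against.** Quits per smoker seen is a recognised public-health measure. It respects randomisation, and higher enrolment is the intended route to benefit. The protocol treats the quitline as evidence-based, so q0 = q1 contradicts its premise. Even with every smoker's status known, the test would reject in only 10% to 20% of trials at q0 = 10%, so no strong randomised cessation test is being passed over. The constant rejection rate is algebra, and Mann-Whitney is only an example.

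Most of this stands. The rate should be kept, and q0 = q1 is only the limiting case. But at q0 = 10% a third of the observed difference (0.21 of 0.62 points) is still not added quitting, and any test of this rate inherits the ambiguity. Counting unobserved smokers as smoking does not help, because the unobserved share differs between arms by design.

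Two stronger readings are tempting. One is that the test has a false-positive rate of 94%. It does not: as a test of quitline-observed quits it keeps its size, and those rejections reflect a real difference in that rate. The other is that Secondary Aim 2 has no analysis at all. The aim and the third hypothesis both refer to per-clinic rates, so the analysis in the plan is plausibly meant for Aim 2. What the documents show is a mismatch of denominators.

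**Conclusion.** The concern holds as a matter of interpretation and of denominator. Quitline-observed abstainers per smoker seen will differ between arms whenever registration differs, so a difference in that rate is not by itself evidence for the third hypothesis.

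The structural point needs no assumed figure. Its size does: 3.5-fold at the planning referral rates with equal enrolment, falling to 1.7-fold if eReferral enrolment is 20%. Rejection of about 94% to 98% rests on the assumed 30% quit probability and between-clinic SD of 2.5 points. At 5% quitting it is about 42% (90 × 6) or 78% (120 × 12).

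The tested denominator also needs reconciling with Secondary Aim 2. The no-overlap expectation is unlikely to be met, but this is minor because Mann-Whitney does not need it. Both primary aims, which concern referral and quality referral, are unaffected. This should be corrected, but it does not threaten the trial's main result.

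**What to change.** 1. Reconcile Secondary Aim 2 with the analytic plan. Analyse the aim as 4-month abstinence among followed registrants, using patient counts by clinic, a model that allows for clustering, and a small-sample correction for 24 clinics. Per-clinic rates alone will not do, since some fax clinics may have no registrants. Label the result imprecise and a comparison of groups formed after randomisation.
2. Keep abstainers per smoker seen, but label it quitline-observed quits (reach plus ascertainment). State that a difference is not by itself evidence for the third hypothesis.
3. Beside it, tabulate added quitting for assumed q0 from 0 up to the enrollee quit rate.
4. Define how rates are projected from up to fifty completers. State that scaling assumes non-completers quit like completers, and show a version counting non-completers as smoking. Give a rule for clinics with registrants but no completer (about 12% of fax clinics at 90 × 6 if half are followed).
5. Remove the no-overlap expectation as the reason for Mann-Whitney.

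Tracking non-registrants through later tobacco status in the EHR would not fill the gap, because quitline data reach the study without patient identifiers.

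Cost: wording, one clustered model and one small table, on data already requested. The price is a weaker cessation claim on a secondary aim and a wide interval for the registrant comparison.
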